9.2. Exploratory Endpoints and Analyses

9.2.1. Anti-Pseudomonas antibiotic sensitivity of *P. aeruginosa* isolates at specified time points during the study

This analysis will be described in a separate plan.

9.2.2. Change in *P. aeruginosa* density from Baseline

Induced sputum culture will be collected as indicated in the Schedule of Assessments in Table 1 of the Protocol Appendix A . Change and percent change in *P. aeruginosa* density (CFU/mL) from induced sputum from Baseline through EOS will be summarized using descriptive statistics at each scheduled time point and will be presented by treatment group. *P. aeruginosa* density count data will be transformed on a log10 scale prior to analysis; summary statistics will display results on the transformed values.

The following data will be excluded from the analysis:

- Data with missing *P. aeruginosa* density count.
- Data with qualitative results (i.e., not quantitative results) due to poor specimen quality.
- Data with specimen condition

In addition to the descriptive summary statistics, figures of *P. aeruginosa* mean density (in original scale and log10 scale) versus time will be developed for each cohort.

This document is confidential.

By subject plot of *P. aeruginosa* density (in original and log10 scale) in induced sputum samples over time will also be developed.

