4 SELECTION AND WITHDRAWAL OF SUBJECTS

4.1 Inclusion Criteria

Subjects who meet all of the following criteria will be considered eligible for enrollment in the study:

1. Are able and willing to comply with the Protocol and provide signed informed consent prior to any study-specific procedures;
2. Are male or female ≥ 18 years old;
3. Have a body mass index of $\geq 16.5 \text{ kg/m}^2$;
4. Have findings consistent with bronchiectasis per computerized tomography (CT) (or high-resolution CT [HRCT]);

Note: A CT or HRCT that demonstrates the above criterion is required during Screening or the Screening Period unless such an examination has been performed within the last 5 years and meets the above criterion.

5. Have microbiological evidence of pulmonary *P. aeruginosa* infection from a sputum sample within the last 24 months. Sputum cultures may be repeated on up to 3 occasions during the Screening Period to document *P. aeruginosa* presence if the initial sputum culture is negative;
6. Are willing and able to provide an induced sputum sample at Screening or during the Screening Period and at designated time points during the study and are willing and able to provide a spontaneously expectorated or induced sputum at all other time points;
7. Have $\geq 10^4$ colony-forming units of *P. aeruginosa* per gram of induced sputum obtained at Screening or during the Screening Period. Up to 3 specimens may be collected to meet this criterion;
8. Have forced expiratory volume (FEV₁) $\geq 35\%$ of predicted normal for age, gender, race, and height (using Global Lung Function Initiative standards) at Screening (regardless of the timing of the most recent prior administration of short-acting bronchodilator) or during the Screening Period;
9. Have, at the Baseline Visit, stable lung function, as determined by the Investigator, provided that the FEV₁ at the Baseline Visit has not decreased by more than 10% compared to the FEV₁ measured at Screening or during the Screening Period;
10. Have no acute infection or exacerbation of primary disease, as determined by the Investigator, prior to randomization and first dose of study drug;
11. Are able to reproducibly perform spirometry per American Thoracic Society/European Respiratory Society Standards;
12. Have past experience administering inhaled antibiotics and/or feel comfortable administering inhaled antibiotics and/or have a caregiver that is comfortable administering inhaled antibiotics to the subject;

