9.2 Statistical Methods

9.2.1 Analysis of Efficacy

9.2.1.1 Efficacy Analyses

The primary efficacy endpoint is the sputum *P. aeruginosa* density as measured in sputum samples at 1 week after end of treatment for study drug (Visit 5/Day 17). The primary efficacy endpoint will be analyzed as logarithmic colony-forming units/g sputum based on the Exploratory Efficacy Population, and the treatment groups will be compared using a 2-sample t test with 0.05 significance level.

In addition, descriptive statistics will be calculated for the primary efficacy endpoint and all the other efficacy endpoints by treatment group based on the Exploratory Efficacy Population.

All statistical summaries will be descriptive in nature (eg, mean, standard deviation, median, minimum, and maximum for continuous variables and count and percentage for categorical variables). Further details, including the handling of missing data, will be specified in the Statistical Analysis Plan (SAP). The actual values and changes from Baseline will be summarized by visit using descriptive statistics, where appropriate, for all endpoints. Analysis details will be provided in the SAP.

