9.1. Primary Efficacy Endpoint and Analysis

The primary efficacy endpoint is change from baseline in *P. aeruginosa* density (CFU/mL) as measured in induced sputum samples at 1 week after end of treatment (Visit 5/Day 17). The endpoint will be analyzed as logarithmic colony-forming units/mL sputum based on the Exploratory Efficacy Population (i.e., CFU counts will be transformed on a log10 scale prior to analysis and the calculation of change from baseline).

Cohort A and Cohort B will be analyzed independently. As there is no adjustment for multiple hypothesis testing only 95% confidence intervals comparing the two treatment groups will be calculated using a 2-sample t test with 0.05 significance level. No p-values will be calculated.

The following data will be excluded from the analysis:

- Data with missing *P. aeruginosa* density count.
- Data with qualitative results (i.e., not quantitative results) due to poor specimen quality.
- Data with specimen condition

A subject may have results from multiple isolates per timepoint. In such cases, *P. aeruginosa* density will be calculated as the sum of *P. aeruginosa* density from multiple isolates per subject per timepoint. Expectorated sputum sample data will not be used for analysis, but the data will be provided in a by-subject listing.

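### As written, SAP 9.2.2 computes percent change in P. aeruginosa density on log10 values, so the figure depends on the starting level and can rank a smaller reduction above a larger one

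*SAP*

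**What the plan says.** SAP 9.2.2 announces summaries of "Change and percent change in *P. aeruginosa* density (CFU/mL) from induced sputum" from Baseline to end of study, by visit and treatment group. Its next sentence fixes the scale: "density count data will be transformed on a log10 scale prior to analysis; summary statistics will display results on the transformed values". Nothing exempts the percent change from that sentence. Original-scale results are planned only for the figures and the by-subject plots.

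SAP 9.1 uses the same order of operations for the same variable: "CFU counts will be transformed on a log10 scale prior to analysis and the calculation of change from baseline". It plans no percentage.

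Protocol 7.1 lists change in density as an exploratory endpoint and does not ask for percent change. Protocol 4.1, criterion 7, requires at least 10^4 "colony-forming units of *P. aeruginosa* per gram of induced sputum obtained at Screening or during the Screening Period", with no upper limit. SAP 7.2.1 takes the last value before the first dose as baseline, and SAP 6.2 requires only that this baseline is not zero.

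**The concern.** A difference of log10 values is the log of a ratio, so it already expresses a proportional change. Zero on the log10 scale is merely 1 CFU per chosen unit. Dividing the difference by the log10 baseline therefore gives a number with no fixed meaning: one and the same reduction yields a different percentage at each starting level.

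Two things are at stake. First, a table column for percent change in density invites reading as the percentage of bacteria removed, and on this scale it falls far short of that. Second, a comparison of subjects or arms on this column mixes the treatment response with the starting level. With about 8 placebo subjects per cohort, some chance imbalance in baseline is to be expected.

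**Working it through.** **Inputs.** From the documents: log10 transformation before analysis (SAP 9.1, 9.2.2); entry floor 10^4 CFU/g, log10 = 4 (Protocol 4.1); 24 subjects per cohort at 2:1 (Protocol 9.2.4), hence 24 × 2/3 = 16 and 24 × 1/3 = 8. Assumed: every baseline other than 10^4, all falls, and the baseline SD. The documents give no density distribution, and the plan states no figure to reproduce.

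**Formulas.**
- Percentage as written: P = 100 × (log10 post − log10 baseline) / log10 baseline
- Actual reduction: R = 100 × (1 − 10^(log10 post − log10 baseline))

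**Step 1: same reduction, different starting level.** A 2-log fall is R = 100 × (1 − 10^−2) = 99% in every row.

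| Baseline | Calculation | P |
|---|---|---|
| 10^4 | −2/4 | −50.0% |
| 10^5 | −2/5 | −40.0% |
| 10^7 | −2/7 | −28.6% |
| 10^9 | −2/9 | −22.2% |

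**Step 2: ranking of individuals.**
- Baseline 10^8, fall of 2.2 log: R = 99.4%, P = −2.2/8 = −27.5%.
- Baseline 10^5, fall of 1.6 log: R = 97.5%, P = −1.6/5 = −32.0%.

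The smaller reduction gets the larger percentage. In general, a fall d1 from log10 baseline b1 ties with a fall d1 × b2/b1 from b2. A 1-log fall from 10^4 thus ties with a 2-log fall from 10^8.

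**Step 3: likely size at arm level.** The standard error of the difference in mean log10 baseline is SD × √(1/16 + 1/8) = 0.433 × SD, which is 0.43 for SD 1 and 0.87 for SD 2. Take two arms with an identical 2-log fall, one with mean baseline 7 and the other one standard error higher, and approximate each arm by its mean baseline:
- Reference arm: −2/7 = −28.6%
- SD 1: −2/7.43 = −26.9%, a shift of 1.7 points
- SD 2: −2/7.87 = −25.4%, a shift of 3.1 points

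If the other arm is lower instead, the values are −2/6.57 = −30.5% and −2/6.13 = −32.6%, shifts of 1.9 and 4.0 points.

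**Step 4: when the arm order reverses.** At SD 1.5 the standard error is 0.65. A one-standard-error imbalance reverses the order only if the larger log fall exceeds the smaller by less than a factor 7.65/7 = 1.09, that is by about 9%. A reversal with clearly different falls needs much more. Suppose the active arm is half at 10^7 and half at 10^8 with a 1.2-log fall: it averages (−17.1 − 15.0)/2 = −16.1%. A placebo arm at 10^5 with a 1.0-log fall gives −20.0%. The gap in mean baseline is 7.5 − 5 = 2.5 log, nearly 4 standard errors at SD 1.5.

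**Step 5: back-transformed alternative.** 100 × (10^(mean log10 change) − 1) gives −99.0% for a 2-log fall and −96.8% for a 1.5-log fall, whatever the baseline.

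**The case against.** The best defence is that little depends on this figure. The endpoint is exploratory and descriptive, and neither document gives the percentage a role in a test, a safety trigger or a dose decision. The log10 change is planned in the same sentence, by visit and arm, with figures on both scales, so the true reduction is not hidden. All of this stands and limits the weight of the point.

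A second defence is that a raw-scale percentage was meant: 9.2.2 does not repeat the 9.1 wording that transformation precedes the calculation of change, and it does plan some original-scale output. That intent is conceivable, but the text points the other way. A raw percent reduction is negative, so it could not itself be shown log-transformed. Either intent calls for an edit.

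Three stronger readings are tempting and not supported:
- *That the percentage distorts a comparison of Cohort A with Cohort B.* SAP 9.1 analyses the cohorts independently, no such comparison is planned, and the documents give no baseline densities for either cohort.
- *That the unit mismatch matters here.* The Protocol specifies CFU/g ("The primary efficacy endpoint will be analyzed as logarithmic colony-forming units/g sputum") and the SAP CFU/mL ("The endpoint will be analyzed as logarithmic colony-forming units/mL sputum"). The percentage does change with the unit in principle, but one unit for all subjects creates no inconsistency between arms. If 1 mL of sputum weighs about 1 g (an assumption), a 10% difference in the factor moves −25.0% only to −24.7% or −25.3%.
- *That the arms will probably be ranked wrongly.* An entry floor shows that wide baselines are possible, not that they occur, and Step 4 shows that reversal needs a large imbalance or nearly equal falls.

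**Conclusion.** The point holds as a defect in a stated rule. On the plain reading of SAP 9.2.2, percent change is divided by the log10 baseline, depends on starting level and can misorder subjects. The dependence is algebraic; the particular values rest on assumed baselines. At arm level, for a 2-log fall around 10^7, a one-standard-error imbalance shifts the summary by about 2 to 3 percentage points when the other arm starts higher (up to 4 when it starts lower), assuming an SD of 1 to 2 log10 and 16 versus 8 subjects. SAP section 6 leaves early lower-dose AP-PA02 subjects out of most summaries, so the active group may be smaller than 16 and the standard error somewhat larger.

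A reader might infer that the efficacy conclusion is at risk. It is not: the primary analysis in 9.1 and the log10 change in 9.2.2 are unaffected. One redundant exploratory summary is misleading and worth correcting because correction is so cheap.

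**What to change.** Either of two edits to SAP 9.2.2 is enough:

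1. Delete the reference to percent change and keep the log10 change by visit and treatment group, which is already planned.
2. If a percentage is wanted, define it as 100 × (10^(mean log10 change) − 1) and label it in the table as the geometric mean percent change.

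If the sponsor intended a percentage on raw CFU values, 9.2.2 should say so explicitly and exempt it from the sentence on transformed values.

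The cost is one line of SAP text and at most one derived column. No new data, visits or subjects are needed.

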9.2.3. Change in spirometry from Baseline

Spirometry analyses are described [Section 10.3](#) of this SAP.

9.2.4. Change from Baseline levels of induced sputum neutrophil elastase

Biomarkers, including induced sputum neutrophil elastase, will be collected at all study visits from Baseline through EOS and tested by the central laboratory. Change from Baseline through EOS will be summarized using descriptive statistics at each scheduled time point and will be presented by treatment group. Subjects with a missing value at Baseline or post Baseline will not be included in the summary from change from Baseline.

9.2.5. Change in quality of life as assessed by the Quality of Life-Bronchiectasis (QOL-B) Questionnaire

The QOL-B Questionnaire is a self-administered PRO measure designed specifically for subjects with bronchiectasis¹, and will be self-administered at Baseline, Visit 4/Day 11, and Visit 6/Day 24. This PRO contains 37 items on 8 scales: Respiratory Symptoms, Physical, Role, Emotional and Social Functioning, Vitality, Health Perceptions, and Treatment Burden. Each of the 37 items are scored from 1-4, and each of the 8 scale scores are standardized on a 0-100 point scale with higher scores indicating fewer symptoms or better functioning and health related QOL. A total score is not calculated.

SAS programming code for calculating scores for the 8 scales is provided in [Appendix 15.1](#). The scaled scores for each of the 8 scales and absolute change from Baseline will be summarized by visit using summary statistics for continuous variables by treatment group.

9.2.6. Change in quality of life as assessed by the Leicester Cough Questionnaire (LCQ)

The LCQ is a 19-item self-completed QOL measure of chronic cough with is responsive to change², and will be administered at Baseline, Visit 4/Day 11, and Visit 6/Day 24. The LCQ contains 19 items which assess three domains: physical (8 items), psychological (7 items), and social (4 items). Subjects will respond to each item using a 7-point Likert response scale.

Questions 1, 2, 3, 9, 10, 11, 14, and 15 comprise the physical domain; questions 4, 5, 6, 12, 13, 16, 17 comprise the psychological domain; and questions 7, 8, 18, 19 comprise the social domain. For each domain, scores are calculated by determining the mean for that domain (sum of scores from items in the domain / number of items in domain; range 1-7). Total LCQ scores are calculated by summing the domain scores (range 3-21).

Physical, psychological, and social domain scores and the Total LCQ score, as well as absolute change from Baseline, will be summarized by visit using summary statistics for continuous variables by treatment group.

9.2.7. Change in quality of life as assessed by the Saint George's Respiratory Questionnaire

The SGRQ is a measure to assess impaired health and perceived well-being (quality of life)³ and will be administered at Baseline and Visit 7 EOS/Day 38. This 14-question questionnaire (40 total items; some questions have multiple items) has 2 parts: Part 1 (questions 1-7) generates the symptom component score, while Part 2 (questions 8-14) generates the activity and impact component scores.^{4,5} A total SGRQ score

This document is confidential.

is also generated. Each possible response to each of the 14 questions is assigned a weight (range 0-100) (Appendix 15.2).

The SGRQ is scored in 2 steps:

- Step 1: Sum weights for all items with a positive response. A positive response is one that shows the presence of symptoms. For example, in Part 1 Question 1, all answers ("Most days a week", "Several days a week" and "Only with respiratory infections") except "Not at all" would be positive. A positive response also has a nonzero score, unlike a negative one. For Part 2 Question 8 ("How would you describe your respiratory problems?"), the following responses are positive: "Cause me a lot of problems or are the most important physical problems I have", "Causes me a few problems"; an answer of "Causes no problem" is negative as it does not show any signs of symptoms. For Part 2 Question 14, any answer except "They do not stop me from doing anything I would like to do" would be considered positive.
 - The symptom component score is calculated by summing weights for questions 1 through 7.
 - The activity component score is calculated by summing weights for positive responses to questions 9 and 12.
 - The impact component score is calculated by summing weights for questions 8, 10, 11, 13, and 14. Note that weights for positive responses to questions 10, 11, and 13 are summed with the response to the single item selected for questions 8 and 14.
- Step 2: Calculate component scores and total score.
 - The score for each component is calculated separately by dividing the summed weights by the maximum possible summed weights for that component and expressing the result as a percentage.
$$\text{Score} = 100 * (\text{summed weights from all positive items in that component} / \text{sum of maximum weights for all items in that component})$$
 - The total score is calculated by dividing the summed weights for all questions by the maximum possible sum of weights and expressing the result as a percentage.
$$\text{Score} = 100 * (\text{summed weights from all positive items in SGRQ} / \text{sum of maximum weights for all items in SGRQ})$$

A total score can be calculated in the presence of missing data, but only if the domains meet the following "missing items" rule. If one domain exceeds its permitted number of missed items, then a total score cannot be calculated.

"Missing items" rules are as follows:

- Symptoms (Questions 1-7)

The symptom component will tolerate a maximum of 1 missed item. The weight for the missed item is subtracted from the total possible weight for the symptom component (566.2) and from the Total weight (3201.9).

This document is confidential.

- Activity (Questions 9, 12; this component has 13 items)

The Activity component will tolerate a maximum of 3 missed items. The weight for the missed item is subtracted from the total possible weight for the Activity component (982.9) and from the Total weight (3201.9).

- Impacts (Questions 8, 10, 11, 13, 14; this component has 20 items)

The Impacts component will tolerate a maximum of 5 missed items. The weight for the missed item is subtracted from the total possible weight for the Impacts component (1652.8) and from the Total weight (3201.9).

Symptom, activity, and impact component scores and the Total score, as well as absolute change from Baseline, will be summarized using summary statistics for continuous variables by treatment group.

This document is confidential.

10. Pharmacokinetics

Pharmacokinetics analyses will be described in a separate plan.

This document is confidential.

11. Safety

The population used for safety analyses will be the Safety Population. Safety will be assessed on the basis of treatment-emergent adverse event (TEAE), vital signs, laboratory assessments, immunogenicity, ECG parameters, and physical examinations.

All safety information will be provided in subject listings.

11.1. Adverse Events / Adverse Drug Reactions

An overall summary of TEAEs will be provided by treatment group and overall, including the number and percentage of subjects who experience at least one of the following:

- TEAEs
- Serious TEAEs
- TEAEs related to study drug
- TEAEs related to study device
- TEAEs related to study procedure
- Serious TEAEs related to study drug
- Serious TEAEs related to study device
- Serious TEAEs related to study procedure
- TEAEs leading to permanent withdrawal of study drug
- TEAEs related to study drug leading to permanent withdrawal of study drug
- TEAEs with Grade 1 (Mild) as Worst Severity
- TEAEs with Grade 2 (Moderate) as Worst Severity
- TEAEs with Grade 3 (Severe) as Worst Severity
- TEAEs with Grade 4 (Life-Threatening) as Worst Severity
- TEAEs leading to death

The number and incidence of events will be provided in the overall summary table by treatment group and overall.

TEAE is defined as an adverse event that was not present prior to administration of the first dose of study drug and subsequently presented after the first dose, or any exacerbation occurring after first dose of an event that was present prior to the first dose.

All AEs will be listed by subject and chronologically by date of AE onset, and by study part, dose group, and subject. The listing will include all data collected in the eCRF and the coded variables. AE dates will be listed as recorded in the eCRF. AEs will be classified by System Organ Class (SOC) and Preferred Term (PT) using MedDRA Version 25.0. Subjects are counted only once within each SOC and PT. TEAEs will be presented by descending frequency by SOC and PT.

Further, the following TEAE summaries will be provided and summarized by treatment group and overall:

- Any TEAEs overall and by SOC and PT
- Serious TEAEs, overall and by SOC and PT
- Study Drug-related TEAEs overall and by SOC and PT
- Study Device-related TEAEs overall and by SOC and PT
- Study Procedure-related TEAEs overall and by SOC and PT

This document is confidential.

- Serious TEAEs related to Study Drug, overall and by SOC and PT
- Serious TEAEs related to Study Device, overall and by SOC and PT
- Serious TEAEs related to Study Procedure, overall and by SOC and PT
- TEAEs by worst severity, overall and by SOC and PT
- Study Drug-related TEAEs by maximum severity, overall and by SOC and PT
- Study Device-related TEAEs by maximum severity, overall and by SOC and PT
- Study Procedure-related TEAEs by maximum severity, overall and by SOC and PT
- TEAEs leading to permanent withdrawal of study drug, overall and by SOC and PT
- Study Drug-related TEAEs leading to permanent withdrawal of study drug, overall and by SOC and PT
- Study Device -related TEAEs leading to permanent withdrawal of study drug, overall and by SOC and PT
- Study Procedure -related TEAEs leading to permanent withdrawal of study drug, overall and by SOC and PT
- TEAEs which resulted in death, overall and by SOC and PT

If a subject has more than one event within a given SOC or PT at different severities, the maximum severity will be tabulated. For example, if a subject experiences two events with the same preferred term, but one was at moderate and the other at severe severity, the severe TEAE will be included in the tabulation. Severity is classified into five categories: mild, moderate, severe, life-threatening, and death.

An AE will be considered drug-related if the relationship attribution is 'possibly related', 'probably related', or 'definitely related' or designation is missing. AEs with a missing onset date, but with stop date either missing or on or after the date of first dose of study drug will be included as treatment emergent. All AEs will be listed in subject listing and summarized by numbers and percent of subjects by dose for each portion of the study separately. If a subject reports the occurrence of a particular event more than once, the most severe of those events will be included in the summary tables of TEAEs, and the most severe of the treatment-related events will be included in the summary tables of treatment-related events.

If the relationship to study drug, study device, or study procedure, is missing for an AE, the event will be assumed to have the maximum relationship (i.e., definitely), respectively. If the seriousness status is missing for an AE, the event will be assumed to be serious.

